2.2.2 Screening activities performed after a consent for screening has been signed

The following activities will be performed only after the subject has signed the consent for this study for screening. Assessments performed at outside facilities or on another NIH protocol within the timeframes below may also be used to determine eligibility once a patient has signed the consent.

2.2.2.1 Laboratory evaluation (needed for eligibility)

- Blood FACS
- CBC with differential
- Creatinine or 24 hour urine for creatinine clearance
- Direct bilirubin, total bilirubin, SGOT and SGPT
- Pregnancy test (urine or serum). Women of childbearing potential must have a negative pregnancy test within 7 days of enrollment.
- Hepatitis B (antigen), hepatitis C and HIV test
- Bone marrow biopsy with IHC for CD20 and CD3. This must have been done since last prior therapy and at least 6 months after prior cladribine.

2.2.2.2 Other evaluations

- EKG
- History & Physical with documented performance status

- CT neck-pelvis or abdominal MRI.

2.3 PARTICIPANT REGISTRATION AND STATUS UPDATE PROCEDURES

Registration and status updates (e.g., when a participant is taken off protocol therapy and when a participant is taken off-study) will take place per CCR SOP ADCR-2, CCR Participant Registration & Status Updates found at: <https://ccrod.cancer.gov/confluence/pages/viewpage.action?pageId=73203825>.

2.3.1 Screen Failures

Screen failures are defined as participants who consent to participate in the clinical trial but are not subsequently assigned to the study intervention or entered in the study. A minimal set of screen failure information is required to ensure transparent reporting of screen failure participants, to meet the Consolidated Standards of Reporting Trials (CONSORT) publishing requirements and to respond to queries from regulatory authorities. Minimal information includes demography, screen failure details, eligibility criteria, and any serious adverse event (SAE).

2.3.2 Treatment Assignment and Randomization Procedures

Cohorts

Number	Name	Description
1	Cohort 1	Patients with HCL with (62 patients) and without (68 subjects) prior course of purine analog to be randomized between Arm 1 and Arm 2 (randomization stratified based upon prior purine analog [yes/no])
2	Cohort 2	Patients with HCL without prior course of purine analog to be directly assigned to Arm 3 (25 patients; after completion of the 68 patients without prior purine analog in Cohort 1)
3	Cohort 3	Patients with HCLv to be directly assigned to Arm 3 (20 patients)

Arms

Number	Name	Description
1	Arm 1	Cladribine + Rituximab
2	Arm 2	Cladribine (+ Rituximab after 6 months if MRD detected)
3	Arm 3	Cladribine + Rituximab (Rituximab will be administered just before rather than after the 1 st of the 5 daily doses of cladribine on day 1)

Stratifications

Name	Distinct Options	Notes

Prior purine analog	Yes No	Applies to Cohort 1 patients randomized between Arm 1 and Arm 2 only (see below).
---------------------	-----------	---

Randomization and Arm Assignment

At the time of registration, patients in Cohort 1 will be randomized between Arm 1 and Arm 2, and patients in Cohort 2 will be directly assigned to Arm 3. Patients with variant HCL (HCLv; Cohort 3) regardless of prior treatment with purine analog are assigned to Arm 3.

- Cohort 1: HCL Patients will be randomized between Arm 1 and 2. Randomization will be stratified on the basis of prior purine analog or not. There will be 68 patients randomized within the no prior purine analog stratum and 62 randomized within the 1+ prior purine analog stratum.
 - Note: The randomization for Cohort 1 will be performed by CRO personnel using randomization assignments generated by the study statistician. The Pharmacy Department will be notified of the treatment assignment once the patient is randomized.
- Cohort 2: 25 patients with no prior purine analog will be assigned directly to Arm 3 following completion of randomization of the 68 patients in the ‘no prior purine analog’ stratum in Cohort 1.
- Cohort 3: Patients with variant HCL (HCLv) regardless of prior treatment with purine analog will be enrolled in this cohort, will not be randomized and will be assigned to Arm 3.

2.4 BASELINE EVALUATION

2.4.1 Prior to treatment (any time)

- Research Blood (and bone marrow if available) for cloning/sequencing IgH rearrangements (multiple sets prior to treatment)
- HLA-A,B,C, DRB,DQB

2.4.2 Day 1 prior to treatment

- CBC with differential
- Needed for patients at NIH: Chemistries (albumin, alkaline phosphatase, ALT, AST, BUN, calcium, CK, chloride, CO₂, glucose, potassium, LDH, magnesium, sodium, phosphorus, total protein, uric acid), urinalysis

2.4.3 Within 4 weeks prior to treatment

- Serum for tumor markers, flow cytometry (FACS), PaxGene tube for RQ-PCR, and citrate tube for consensus PCR, ferritin, IgG, IgA, IgM, PT, PTT, fibrinogen, haptoglobin, amylase, lipase, GGT, free T3, free T4, quantification of T, B and NK cells (TBNK), C-reactive protein (CRP), thrombin time. Pregnancy test (if relevant) needed with 1 week prior to enrollment.

Note: tubes and media may be substituted based on availability with the permission of the PI or laboratory investigator.

- Abdominal ultrasound (U/S) – may do spleen U/S instead per PI discretion.

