1.3.11 Relationship of this trial to current research performed in LMB

The Laboratory of Molecular Biology (LMB) is currently developing recombinant immunotoxins for treating several forms of cancer, and the most successful trials have been performed in patients with HCL [35-38]. A major and increasing focus of the lab is in studying MRD after treatment for HCL using the highly sensitive RQ-PCR assay, and this assay has already been used to study MRD after purine analog and rituximab [48]. The lab is also studying the biology of HCL through patient samples obtained and has the largest molecular database of HCL patients reported [66-68]. Patient recruitment for HCL trials has been very strong and the growing population of untreated patients seeking advice indicates that a trial earlier in the disease would also accrue well at NIH. In addition to the RQ-PCR assay in the LMB which needs to be tested after agents other than immunotoxins, the Laboratory of Pathology has excellent tools for studying HCL MRD, including flow cytometry, consensus PCR, and immunohistochemistry [46, 48]. Finally, this trial can benefit the LMB immunotoxin program by identifying a group of patients eligible in the near future for immunotoxin trials. Recombinant immunotoxin HA22 [69], an improved version of BL22, is the agent now being developed for treatment of cladribine-resistant HCL. The phase II trial of BL22 in patients with HCL showed that tumor burden affected response. For example, patients with spleens < 200 mm had a 95% overall response rate (ORR), compared to 20% (p = 0.001) in patients with larger spleens or 33% (p = 0.0007) in patients post splenectomy. These results argue that close follow-up of HCL patients after standard therapy and treatment with BL22 in early relapse may be beneficial. Thus an added benefit of this trial will be the ability to prospectively follow a large number of HCL patients after standard therapy, monitoring for early relapse. These patients may be eligible for a pivotal study of an immunotoxin for HCL.

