6.2 SECONDARY ENDPOINTS

In addition to the primary goal of determining differences in the MRD level according to rituximab administration, the following goals will also be explored in patients on this study.

The most important secondary endpoints are MRD-free survival after cladribine, and MRD-free survival after up to 2 courses of rituximab. For the secondary endpoints of this protocol, and for triggering delayed rituximab, patients with or without CR are considered MRD+ if the blood FACS is positive or if low blood counts become inconsistent with CR (ANC < 1500/ μ l, Plt < 100,000/ μ l, or Hgb < 11). Patients FACS-negative in both blood and bone marrow aspirate are considered MRD-negative regardless of blood counts. Failure of cladribine and/or rituximab to clear MRD by blood FACS requires that this test be positive at 6 months since MRD at 1-3 months may clear by 6 months. However, MRD relapse will be considered when first detected, even if before 6 months, if cladribine and/or rituximab fail to clear MRD at 6 months. If simultaneous cladribine and rituximab is superior to cladribine and delayed rituximab, MRD-free survival after cladribine and after delayed rituximab should together be longer if cladribine was combined with rituximab than if used alone. In order to compare the probability of development of MRD as a function of time according to whether rituximab is used immediately or not, Kaplan-Meier curves for this endpoint will be created, beginning at the date of randomization, and compared using a two-tailed log-rank test. Patients who develop MRD will be considered to have had an event for the actuarial curve, while those without MRD found in this manner will be considered censored and will remain in follow-up for this endpoint. With each stratum considered separately, or if both strata are combined, the power for this comparison will potentially be low, but the results may demonstrate a trend if one is present. Measurement of best response to cladribine vs. cladribine + rituximab will also be done at 1 and 6 months after cladribine. The CR and PR rates will be reported, as well as appropriate 95% exact confidence intervals.

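### The MRD-free survival comparison in 6.2 uses no baseline tumor burden measure, although soluble markers are collected in every patient: a valid test, but possibly an inefficient one

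*Combined protocol and SAP*

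**What the plan says.** Section 6.2 ranks the endpoint high: "The most important secondary endpoints are MRD-free survival after cladribine, and MRD-free survival after up to 2 courses of rituximab". For the comparison between arms, "Kaplan-Meier curves for this endpoint will be created, beginning at the date of randomization, and compared using a two-tailed log-rank test". It allows for analysis in two ways ("With each stratum considered separately, or if both strata are combined") and concedes that "the power for this comparison will potentially be low". It gives no hazard ratio, event count, significance level or power figure, and names no regression model, stratified test or baseline covariate.

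Section 2.4.3 lists, within 4 weeks before treatment, "Serum for tumor markers, flow cytometry (FACS), PaxGene tube for RQ-PCR, and citrate tube for consensus PCR". The first footnote to the calendar in 15.1.1 applies the baseline tests to all patients. Section 1.1.2 identifies the tumor markers as soluble CD25 and CD22, and 1.3.9 describes soluble CD22 as quantifying tumor burden. Their planned uses are correlative: 1.1.2 concerns levels after treatment, and 6.2 lists marker correlations as a separate secondary aim. Randomization is stratified on prior purine analog only (2.3.2).

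**The concern.** With 34 or 31 patients per arm in a stratum, baseline burden is balanced only by chance. If it predicts time to MRD, a test that ignores it has less power than an analysis that conditions on it. The comparison matters: 1.3.2 says that a difference at 6 months would not by itself show a better clinical outcome, and makes blood MRD-free survival the major secondary endpoint. An inconclusive result there would leave the question of simultaneous versus delayed rituximab open, while a measurement that might have sharpened the answer was already in hand.

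**Working it through.** **1. The plan's own power figure.** Section 6.1 states 80% power per stratum for the primary test (one-sided Fisher's exact, 0.1). Summing the binomial probabilities of all outcome pairs with one-sided p ≤ 0.1 gives 80.6% (34 per arm, 5% v 25%) and 80.3% (31 per arm, 10% v 35%). The figure reproduces. The log-rank comparison inherits this sample size and has no power statement of its own.

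**2. Power of the log-rank test.** Schoenfeld's formula is power = Φ(|ln HR|·√d/2 − 1.96), with d events, 1:1 allocation and two-sided 0.05 (assumed). With 50% of patients having events (assumed):

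| Patients | Events | HR 0.5 | HR 0.6 | HR 0.7 |
|---|---|---|---|---|
| 68 | 34 | 52% | 32% | 18% |
| 62 | 31 | 49% | 30% | 17% |
| 130 | 65 | 80% | 54% | 30% |

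For example, with 65 events and HR 0.5: 0.693 × 8.06/2 − 1.96 = 0.83, and Φ(0.83) = 80%. The plan's caution about power is therefore fair unless the effect is strong or most patients have events.

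**3. Adding one baseline covariate.** The data were simulated with exponential times, administrative censoring, a standard-normal covariate and 3,000 trials per setting (Monte Carlo error about 1 point). Each cell gives log-rank → adjusted Cox power, in %, by covariate HR per SD:

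| Patients, event fraction, treatment HR | 1.0 | 1.5 | 2.0 | 2.5 |
|---|---|---|---|---|
| 130, 50%, 0.5 | 79.7 → 78.8 | 74.7 → 78.3 | 65.9 → 77.8 | 61.0 → 78.4 |
| 130, 70%, 0.5 | 90.5 → 90.3 | 86.5 → 90.3 | 77.4 → 89.5 | 68.6 → 89.7 |
| 130, 50%, 0.6 | 55.2 → 54.4 | 49.0 → 53.0 | 43.5 → 52.8 | 36.9 → 52.3 |
| 130, 70%, 0.6 | 69.8 → 69.2 | 59.8 → 66.4 | 50.7 → 67.4 | 43.4 → 66.0 |
| 68, 50%, 0.6 | 32.6 → 31.3 | 30.0 → 31.0 | 25.1 → 30.9 | 23.0 → 31.1 |

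Under no treatment effect, type I error was 4.4–5.6% for the log-rank test and 4.5–5.8% for the adjusted Cox model.

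**4. The same with the trial's strata.** Strata of 68 and 62 were used, with assumed control hazards of 0.12 and 0.22 per year, censoring uniform over 2 to 8 years, and treatment HR 0.5. Both analyses are stratified by prior purine analog, so the gain is due to the covariate alone. Unadjusted v adjusted power:
- 1.0 per SD: 74% v 75%, and 72% v 72% in an independent run
- 1.5 per SD: 69% v 72%, and 70% v 74%
- 2.0 per SD: 62% v 72%, 60% v 72% and 63% v 74%

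**5. Stronger treatment effects.** The planned 6-month rates correspond to early HRs of ln 0.95/ln 0.75 = 0.18 and ln 0.90/ln 0.65 = 0.24. The mapping is approximate, because the primary endpoint uses three tests and this one is based on blood. In the model of step 4 at 2 per SD, HR 0.25 gives 99.1% v 99.8%, and HR 0.35 gives 91% v 96% (800 trials each). Allowing for simulation error, the gain is about 1 to 6 points.

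**6. Chance imbalance.** The SD of the difference in covariate means is √(2/34) = 0.24 SD in the larger stratum and √(2/65) = 0.18 SD overall. At 2 per SD, one such deviation shifts the HR by a factor of 2^0.24 = 1.18 or 2^0.18 = 1.13. The test's type I error already allows for this.

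**The case against.** The strongest objection is that no prognostic effect on this endpoint has been shown. A reader might infer from 1.3.11, where the BL22 trial "showed that tumor burden affected response", that the plan's own evidence makes burden a strong predictor here. It does not. Those data concern another agent, given after an inadequate response to purine analog, and a response endpoint. They also do not run steadily with spleen size: response was 95% with spleens under 200 mm, 20% with larger ones, and 33% after splenectomy. Spleen size is undefined for the last group, and coding it as small would place poor responders with the best. Section 1.3.9 says only that soluble CD22 may help to predict early relapse. This objection stands, and it is why the gain can be given only as a range.

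A second objection is that the simulated hazards do not match the plan. They give 1 − e^(−0.06) = 5.8% and 1 − e^(−0.11) = 10.4% of control patients with events by 6 months, against planned MRD rates of 25% and 35%. Subject to the mapping caveat in step 5, this also stands: with an effect as large as planned, little power is left to gain.

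A reader might also infer that the unadjusted analysis is biased. In step 4 at 2 per SD, the unadjusted HR averages 0.54 to 0.55 when the conditional HR is 0.50. These are two different estimands, the planned log-rank test reports no HR, and randomization keeps it valid.

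It is fair, too, that a Cox HR brings in proportional hazards. Failure to clear MRD concentrates events by 6 months, with slower relapse afterwards, so the assumption may fail. Finally, 6.2 calls the secondary analyses exploratory. Its remark about reporting them without formal adjustment most naturally concerns multiplicity and does not settle the covariate question.

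**Conclusion.** The point holds as a missed efficiency in an important but exploratory comparison. It is not an error in the test, and it does not touch the primary analysis. With all 130 randomized patients and a treatment HR of 0.5, the gain in power is about 0 points if the covariate is not prognostic, roughly 3 to 5 at 1.5 per SD, and roughly 10 to 12 at 2 per SD. With a treatment HR of 0.25 to 0.35 and 2 per SD, it is about 1 to 6 points. It can be larger for weaker effects with many events (16.7 points at HR 0.6, 70% events, 2 per SD). Across the settings in step 3, the cost of a useless covariate was at most 1.4 points. Adjustment does not rescue a single small stratum: with 68 patients, 50% events and HR 0.6, adjusted power is about 31%. The treatment HRs, event fractions, hazards, covariate strengths and two-sided 0.05 level are all assumptions; the documents give none of them for this comparison.

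**What to change.** In 6.2, keep the Kaplan-Meier curves and the log-rank test. Add one pre-specified analysis: a Cox model stratified by prior purine analog, with treatment arm and a single named covariate, log baseline soluble CD22, reporting the adjusted HR with its 95% CI. State that this HR is conditional on the covariate, that proportional hazards will be checked, and that the log-rank result stands if the check fails.

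Fix the covariate before any comparison of this endpoint by arm, and record the date. This matters because 6.3.1 already reports a 6-month MRD count for one randomized group (1 of 27), and an open choice between markers would invite selection after the fact. Do not enter spleen size as a linear term unless splenectomized patients form a separate category.

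The cost is one paragraph of analysis text. The sample is already scheduled before treatment in all patients.

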2.4.4 Within 28 days from starting delayed rituximab

- HCL Imaging, EKG, amylase, lipase, GGT, lipid panel, TSH, free T3, free T4, ferritin, PCR, IgG, IgA, IgM, haptoglobin, CRP, urinalysis, and chemistries

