2.1.1.5 No prior rituximab unless HCLv patient

2.1.1.6 ECOG performance status [78] of 0-3 (see [Appendix C](#)).

2.1.1.7 Patients must be able to understand and give informed consent.

- 2.1.1.8 Women of child-bearing age and all men must use birth control of any type until at least 12 months after the last dose of therapy.
- 2.1.1.9 Creatinine \leq 1.5 or creatinine clearance \geq 60 ml/ml.
- 2.1.1.10 Bilirubin \leq 2 unless consistent with Gilbert's (total/direct $>$ 5), ALT and AST \leq 2.5 x upper limits of normal.
- 2.1.1.11 No other therapy (i.e. chemotherapy, interferon) for 4 weeks prior to study entry, or cladribine for 6 months prior to study entry.
- 2.1.1.12 Age at least 18
- 2.1.1.13 Men and women of reproductive potential must agree to use an acceptable method of birth control during treatment and for twelve months after completion of treatment.
- 2.1.1.14 Subject has provided written informed consent
- 2.1.1.15 Patients must be willing to co-enroll in the investigator's companion protocol 10-C-0066 titled "Collection of Human Samples to Study Hairy Cell and other Leukemias, and to Develop Recombinant Immunotoxins for Cancer Treatment".

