2.1.2 Exclusion Criteria

- 2.1.2.1 Presence of active untreated infection
- 2.1.2.2 Uncontrolled coronary disease or NYHA class III-IV heart disease (see [Appendix D: New York Heart Association Classification](#)).
- 2.1.2.3 Known infection with HIV. Hepatitis B is allowed only if viral load is undetectable and if on anti-hepatitis B therapy like Entecavir. Hepatitis C is allowed only if viral load is undetectable, and if the patient has received curative therapy.
- 2.1.2.4 Patients with documented history of no response to cladribine, and without 50% improvement in platelets, hemoglobin or granulocytes. This exclusion does not apply to HCLv. These patients are eligible regardless of prior response to CDA.
- 2.1.2.5 Pregnant or lactating women.
- 2.1.2.6 Presence of active 2nd malignancy requiring treatment. 2nd malignancies with low activity which do not require treatment (i.e. low grade prostate cancer, basal cell or squamous cell skin cancer) do not constitute exclusions.
- 2.1.2.7 Inability to comply with study and/or follow-up procedures.
- 2.1.2.8 Presence of CNS disease, which is symptomatic.
- 2.1.2.9 At the Investigator's discretion, receipt of a live vaccine within 4 weeks prior to randomization. Efficacy and/or safety of immunization during periods of B-cell depletion have not been adequately studied. It is recommended that a patient's vaccination record and possible requirements be reviewed. Per the investigator's discretion, the patient may have any required vaccination/booster administered at least 4 weeks prior to the initiation of study treatment. Review of the patient's immunization status for the following vaccinations is recommended: tetanus; diphtheria; influenza; pneumococcal polysaccharide; *Varicella*; measles, mumps and rubella (MMR); and hepatitis B. Patients who are considered to be at high risk for hepatitis B virus (HBV) infection and for whom

the investigator has determined that immunization is indicated should complete the entire HBV vaccine series at least 4 weeks prior to participation in the study.

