3.8.1 Criteria for removal from protocol therapy

- Voluntary patient withdrawal
- Non-compliance with treatment and tests (discretion of PI)
- The patient has received 16 infusions of rituximab
- Progressive disease after the 2nd course of rituximab
- Progression prior to finishing 2 courses of rituximab which is considered by the PI to be too rapid to treat with rituximab alone.
- Dose-limiting toxicity
- Intercurrent illness or medical circumstances making it unsafe to remain on treatment
- Radiation therapy
- Positive pregnancy test

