15.1.1 Early Rituximab with Cladribine or Cladribine alone

Time point	Pre ¹	d1	d2	d3	d4	d5	w2	w3	w4	w5	w6	w7	w8
Treatment													
Cladribine		X	X	X	X	X							
Rituximab (if receiving)		X					X	X	X	X	X	X	X
Procedures													
Bone Marrow Biopsy ³ , MRI ⁵	X									X			
Echocardiogram, stress test, PFTs	X												
Abdominal/splenic ultrasound	X												
HCL Imaging ⁴	X									X			
EKG	X									X			
History & Physical	X									X			
Laboratory Evaluation													
HBsAg, HBeAg, & HCV, HIV, SPEP/immunoelectrophoresis, serum	X												
24hr urine protein, creatinine clearance & UPEP	X												
FACS, amylase, CRP, lipase, lipid panel, GGT, TSH, free T3, free T4, TSH, ferritin, PCR consensus, IgG, IgA, IgM, D-Dimer, thrombin time, haptoglobin, fibrinogen	X									X			
PT, PTT	X												
Pregnancy test (if relevant)	X												
TBNK ²	X					X ²	X ²	X ²	X ²	X	X ²	X ²	X ²
CBC, diff	X	X ⁹	X	X		X ¹¹	X ²	X ²	X ²	X	X ²	X ²	X ²
Urinalysis, chemistries ⁶	X	X ²	X	X		X				X			
Research Evaluations⁸													
Tumor Markers	X					X ²	X ²	X ²	X ²	X	X ²	X ²	X ²
HLA-A,B,C, DRB,DQB, research blood (PBMCs)	X												
PaxGene	X									X			
Thrombomodulin, P-selectin, plasminogen activator inhibitor type 1, vWF activity, vWF antigen, d-dimer, FDP, fibrinogen, retic, LDH, haptoglobin		X ^{2,10,11}	X ^{2,11}	X ^{2,11}		X ^{2,11}							

Time point	Pre ¹	d1	d2	d3	d4	d5	w2	w3	w4	w5	w6	w7	w8
Cytokine Panel 13 ⁷		X ^{2, 9}	X ²										

¹ Refer to Section 2.4 for timing of baseline studies. All patients will have baseline testing performed as outlined in this calendar.

² When patients are at NIH

³ At NIH, if not already done within 6 months from starting delayed rituximab aspirate for FACS, PCR-molecular diagnostics, and cloning/sequencing IgH rearrangements.

⁴ CT neck-pelvis or abdominal MRI needed only before cladribine. If no nodes, all subsequent imaging may be done with spleen U/S (or abdominal U/S if no spleen), including baseline for delayed rituximab

⁵ MRI of C- and T-Spine (only at NIH) may be cancelled at discretion of PI. MRI may be performed on all randomized and HCLv patients. Non randomized HCL classic patients will not have research MRIs performed

⁶ Chemistries=albumin, alkaline phosphatase, ALT, AST, bilirubin, BUN, calcium, CK, chloride, CO2, creatinine, direct bilirubin, glucose, potassium, LDH, magnesium, sodium, phosphorus, total protein, uric acid

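### No pregnancy test is scheduled before delayed rituximab, although pregnancy is an exclusion and a positive test is a removal criterion, and the contraception period is ambiguous between courses

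*Combined protocol and SAP*

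**What the plan says.** Pregnancy enters the protocol in three ways.

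- **Eligibility and removal.** Section 2.1.2.5 excludes "Pregnant or lactating women". Section 3.8.1 lists "Positive pregnancy test" among the grounds for removal from protocol therapy.
- **Testing.** Section 2.2.2.1 states: "Women of childbearing potential must have a negative pregnancy test within 7 days of enrollment". Section 2.4.3 repeats the timing: "Pregnancy test (if relevant) needed with 1 week prior to enrollment". Calendar 15.1.1 has one pregnancy-test row with a single mark, read as the pre-treatment column.
- **Contraception.** Section 2.1.1.8 covers every man, and those women who are of child-bearing age; its wording is that they "must use birth control of any type until at least 12 months after the last dose of therapy". Section 2.1.1.13 covers participants of either sex with reproductive potential; its wording is that they "must agree to use an acceptable method of birth control during treatment and for twelve months after completion of treatment".

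For delayed rituximab, section 2.4.4 gives an itemised list for the 28 days before the course: "HCL Imaging, EKG, amylase, lipase, GGT, lipid panel, TSH, free T3, free T4, ferritin, PCR, IgG, IgA, IgM, haptoglobin, CRP, urinalysis, and chemistries". Calendar 15.1.2 restarts with each delayed course, and calendar 15.1.3 governs follow-up. Section 3.2.2 allows delayed rituximab from 6 months onward once blood FACS is positive, and sets no latest date. Beyond 2.5 years, calendar 15.1.3 continues FACS annually.

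**The concern.** Patients are treated at widely separated times. Those given early rituximab may have one delayed course, and those randomized to cladribine alone may have two. The protocol treats each delayed course as a fresh baseline. Section 2.4.4 repeats imaging, EKG and a long laboratory panel, calendar 15.1.2 calls for a new marrow if the last is more than 6 months old, and section 5.1.1 does not let pre-enrollment signs and symptoms serve as the baseline for a delayed course. Pregnancy status can change in the interval and is tied to a removal criterion, yet it is not on the list.

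A site that follows the lists exactly could therefore start an eight-infusion course with pregnancy status known only from enrollment, possibly years earlier. The protocol itself recognises fetal exposure as a hazard: the definition of a serious adverse event in section 11.1 includes harm to a child or fetus exposed before conception or during pregnancy. What is at stake is participant safety, not the trial's inference.

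**Working it through.** The plan states no figure on this point to reproduce. The check is a side-by-side reading of the schedules, followed by one date calculation.

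**Step 1. Where a pregnancy test is scheduled**

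- Screening, 2.2.2.1: yes, within 7 days of enrollment.
- Baseline, 2.4.3: yes, within 1 week before enrollment.
- Calendar 15.1.1: one mark, pre-treatment.
- Before delayed rituximab, 2.4.4: none.
- Calendar 15.1.2, repeated for each delayed course: none. The footnoted definition of chemistries does not include one.
- Follow-up calendar 15.1.3: none.

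Scheduled tests after enrollment: 0, however the contraception wording is read.

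**Step 2. When the contraception period ends, if counted from the most recent course**

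Inputs: cladribine on days 1 to 5; eight weekly rituximab doses from day 1 (3.2); 12 months (2.1.1.8, 2.1.1.13); about 30.4 days per month. Formula: end of period = time of last dose + 12 months, counted from day 1.

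- Cladribine alone: last dose on day 5, which is 4 / 30.4 = 0.1 months. The period ends at about month 12.1.
- Cladribine plus rituximab on schedule: dose 8 falls on day 1 + 7 × 7 = 50, which is 49 / 30.4 = 1.6 months. The period ends at about month 13.6.

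**Step 3. Compare with the protocol's own examples (Appendix B)**

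- Example B (early rituximab, delayed course at month 16): 16 − 13.6 = 2.4 months after the period ends.
- Example B, if the last early dose slipped by the 12 weeks that section 3.3.1 permits: 84 / 30.4 = 2.8 months, so the period ends at 13.6 + 2.8 = 16.4 months and the course is covered.
- Example C (early rituximab, delayed course at month 6): inside 13.6.
- Examples D and E (cladribine alone, delayed courses at months 6 and 12): inside 12.1, E only just.
- Example F (cladribine alone, delayed courses at months 10 and 17): the first is inside 12.1. Its last dose falls at about 10 + 1.6 = 11.6, so the period then runs to about 23.6 and the second course is inside.

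On this reading, one of the six delayed courses illustrated falls outside the period. Any first delayed course after about month 12.1 in the cladribine-alone arm would also fall outside it.

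**Step 4. The other reading**

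If the 12 months run from the last dose the protocol may ever give, the duty continues between courses and there is no contraception gap. Neither criterion says which reading is meant. Step 1 does not depend on the answer.

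**The case against.** Several stronger readings are tempting, and the case against them is good.

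- **A reader might infer that the removal criterion cannot operate.** Section 3.8.1 does not require the positive result to come from a scheduled test. A clinically prompted test would trigger it, the section also has a general ground for circumstances that make treatment unsafe, and calendar 15.1.2 requires a history and physical when MRD is detected. What is missing is a scheduled source for the result.
- **A reader might infer that contraception certainly lapses before delayed rituximab.** Delayed rituximab is protocol therapy, section 2.1.1.13 applies during treatment, and section 2.1.1.8 sets a minimum. The text permits a reading with no lapse, so the finding is ambiguity.
- **A reader might use the 53 and 23 months in section 6.1 to say that many delayed courses fall outside the period.** Those are historical durations after cladribine: a median CR duration in untreated patients and a response duration in pretreated ones. They are not times to blood FACS positivity, and section 3.1.3 says blood MRD-free survival is usually shorter than disease-free survival. Five of the six illustrated courses fall inside the period. The examples are illustrations and not frequencies, so they do not show that the gap is rare either.
- **A reader might count all 175 evaluable patients as exposed.** The test concerns only women of childbearing potential, and their number is not given.
- **A reader might call the two contraception criteria contradictory.** They differ in who is covered and in the method required, but a participant can satisfy both. The wording is redundant and unclear, not impossible to follow.

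None of this supplies a scheduled test after enrollment, and none of it says which course the 12 months are counted from.

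**Conclusion.** The point holds as a gap between the schedule and the protocol's own criteria. No pregnancy test is scheduled after enrollment, while delayed rituximab may begin at any time from 6 months onward, so the removal criterion in section 3.8.1 can then act only on an unscheduled test. This rests on the text alone.

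The contraception part is conditional. Counted from the most recent course, and with early doses on schedule, the duty ends at about month 12.1 or 13.6, and Example B starts about 2.4 months later. Counted from the last course the protocol may give, there is no gap.

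The number of people affected cannot be estimated from the documents. The primary MRD comparison and the sample size are unaffected: the primary assessment is at 6 months, within the contraception period on either reading. The text available for this check did not include Appendix F or the consent form, so wording there was not considered.

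**What to change.** The sponsor should reconcile section 2.4.4 and calendars 15.1.2 and 15.1.3 with sections 2.1.2.5, 2.1.1.8, 2.1.1.13 and 3.8.1, so that the schedule for delayed courses is consistent with the pregnancy exclusion and the removal criterion. The contraception period should be stated once, with the course it is counted from made explicit. The clinical rule is for the sponsor to choose, and none is proposed here.

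The cost is a protocol and calendar amendment. Any added assessment would fall at a visit that already collects blood and urine, so the extra work is minor. No change to the statistical analysis is needed.
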